### 4.2.5 Biomarker

The biomarker endpoints are exploratory summaries for [REDACTED] CA125, and CA19-9.

[REDACTED]

## 5 SAMPLE SIZE AND POWER

Dose Escalation: In the dose escalation part of the study, i.e., both Part 1A and 1B, the sample size per dose level cannot be precisely determined but depends on the observed DLTs and the decision rules of mTPI. Between 2 and up to 13 DLT evaluable subjects may be enrolled to a given cohort. Treating additional subjects beyond the 13 would be unlikely to alter the decision specified by the mTPI algorithm.

Cohort Expansion: During this part of the study approximately 25 subjects with high expression of mesothelin are expected to be treated in each tumor cohort at the maximally administered dose or at a dose near the MTD (as determined from dose escalation). This number is based on achieving a reasonable precision of the objective response rate (ORR) and adequate control on the false negative rate (FNR) and false positive rate (FPR) (assuming a historic and target response rate). In a cohort of 25 marker positive subjects if 5 or 6 responses are observed (e.g. for gastric or pancreatic cohorts) then the ORR 90% CI are (8.2%, 37.5%) and (11%, 42%), respectively. If 7 responses are observed (e.g. NSCLC cohort), then the 90% CI is (14%, 46.2%), and if 8 or 9 responses are observed (e.g. mesothelioma or ovarian cohorts), then the 90% CI for ORR are: (17%, 50.4%) and (20%, 54.4%), respectively. These calculations are based on the Clopper- Pearson method for exact confidence intervals.

In addition, 25 subjects per cohort provide the following FNR and FPR under assumptions of expected true ORR. If the true objective response rate (ORR) is 40% (e.g. mesothelioma and ovarian cohorts), then with 25 subjects in a cohort there is 97% and 93% chance of observing at least 6 or 7 responses, respectively, and there is 7% chance of observing 6 or fewer responses (false negative rate). If the true ORR for these tumors is only 20% (rather than 40%), then there is 22% and 11% chance respectively of observing at least 7 and at least 8 responses among 25 subjects (false positive rate).

Similarly if the true ORR is 20% (e.g. gastric and pancreatic cohorts), then there is 97% and 90% probability of observing at least 2 or 3 responses respectively, among 25 subjects and 10% of observing 2 or fewer responses (false negative rate). If the true ORR for these tumors is 10% (rather than 20%) then there is 24% and 10% chance respectively, of observing at least 4 and at least 5 responses (FPR).

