#### **3.1.2 Dose Expansion (Part 2)**

The purpose of the cohort expansion will be to assess preliminary antitumor efficacy, expanded safety experience, and PD effects of BMS-986148. Additional subjects will be treated after the completion of Part 1A and/ or Part 1B, at the MTD, or at an alternative dose below MTD as agreed upon by the BMS Medical Monitor and investigators. Part 2 can begin before the completion of Part 1B as the Q3W dosing regimen is the intended regimen for Part 2. However, if the aggregate PK and safety data indicate similar safety but higher cumulative exposure with the QW dose schedule, this schedule may also be evaluated in Part 2 in an additional cohort of 25 to 26 subjects, once the MTD or a tolerated dose below the MTD is identified in Part 1B. Treatment doses in the cohort expansion groups will not exceed the MTD.

Five expansion cohorts will be restricted to these tumor types 1) mesothelioma 2) pancreatic 3) ovarian 4) NSCLC, and 5) gastric cancer. Enrollment in cohort expansion will be determined by the mesothelin expression of the archived tumor sample (or fresh tumor sample if archived sample is not available).

The enrollment in each expansion cohort will be guided by a Simon 2-Stage design framework (see [Table 8.1-1](#)) exploring efficacy in the following 2 populations: [REDACTED]

Anti-tumor activity will be assessed initially in approximately 12 to 15 evaluable subjects per tumor type (Stage 1) treated in each monotherapy cohort, with the option to stop enrolling in a cohort without an initial anti-tumor activity signal. The number of subjects needed for the Stage 1 review is guided by a Simon 2-Stage design as shown in Table 8.1-1 below for each tumor type with futility boundaries as follows: after Stage 1, if none of the first 15 evaluable subjects in the gastric or pancreatic cohorts, if  $\leq 2$  of the first 12 with mesothelioma, or  $\leq 1$  of the first 14 with NSCLC or ovarian cohort demonstrate clinical activity, enrollment in the cohort meeting criteria may be stopped for this population.

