In addition, 25 subjects per cohort provide the following FNR and FPR under assumptions of expected true ORR. If the true ORR is 40% (eg, mesothelioma), then with 25 subjects in a cohort there is 97% and 93% chance of observing at least 6 or 7 responses, respectively, and there is 7% chance of observing 6 or fewer responses (FNR). If the true ORR for this tumor is only 20% (rather than 40%), then there is 22% and 11% chance respectively of observing at least 7 and at least 8 responses among 25 subjects (FPR).

Similarly if the true ORR is 20% (eg, gastric and pancreatic cohorts), then there is 97% and 90% probability of observing at least 2 or 3 responses respectively, among 25 subjects and 10% of observing 2 or fewer responses (FNR). If the true ORR for these tumors is 10% (rather than 20%) then there is 24% and 10% chance, respectively, of observing at least 4 and at least 5 responses (FPR).

If the true ORR is 30% (eg, NSCLC and ovarian cohorts), then there is 91% and 81% probability of observing at least 5 or 6 responses, respectively, in 25 subjects and 9% of observing 5 or fewer responses (FNR). If the true ORR for these tumors is 15% (rather than 30%) then there is 16% and 7% chance, respectively, of observing at least 6 and at least 7 responses (FPR).

The Simon 2-Stage design will be used in the monotherapy and nivolumab combination expansion cohorts, with a minimum of subjects treated initially as per the Stage 1 n of [Table 8.1-1](#) and [Table 8.1-2](#) below. Efficacy will be explored in both the [REDACTED] populations; there will be no adjustment for multiple comparisons. In each of monotherapy or combination cohorts after a minimum number of subjects (n for Stage 1) are treated, there will be an initial evaluation of efficacy independently in each cohort. If there is a lack of signal in either population, then treatment in that cohort may be stopped in that population; if there is an initial efficacy signal, subjects will continue to be treated in Stage 2 for the population in which there was a signal. [REDACTED]

The above results will inform potential early decisions and guide planning/operations or early termination after taking into consideration additional data, for example, duration of response

and/or SD and safety. The operational characteristics of these Simon 2-Stage designs are provided in the following tables.

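### SAP Section 5 states the ovarian cohort's error rates for a 20% versus 40% response rate, but the protocol designs that cohort on 15% versus 30%, so the stated rates do not apply to it

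*SAP*

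**What the plan says.** **SAP, Section 5.** The planned size is given as "approximately 25 subjects with high expression of mesothelin are expected to be treated in each tumor cohort". Ovarian appears twice, each time beside mesothelioma:

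- Precision example: "if 8 or 9 responses are observed (e.g. mesothelioma or ovarian cohorts".
- Error rates: "If the true objective response rate (ORR) is 40% (e.g. mesothelioma and ovarian cohorts", followed by "there is 7% chance of observing 6 or fewer responses (false negative rate". The contrasting rate is then introduced: "If the true ORR for these tumors is only 20% (rather than 40", and the result is "there is 22% and 11% chance respectively of observing at least 7 and at least 8 responses among 25 subjects (false positive rate".

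The only other pair of rates with error probabilities is 20% versus 10%, for gastric and pancreatic. NSCLC has a precision example at 7 responses and no error rates. Section 5 does not mention the two-stage design.

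**Protocol, Section 8.1.** The 40% versus 20% contrast is given for mesothelioma alone. Ovarian is placed with NSCLC: "If the true ORR is 30% (eg, NSCLC and ovarian cohorts", against 15%, with false-positive rates of 16% and 7% at 6 or more and 7 or more of 25, and a precision example at 7 responses. Table 8.1-1 gives ovarian monotherapy as historic 15%, target 30%, 14/26, Stage 1 boundary 1, alpha 0.18, power 0.82, early stopping 0.36. The ovarian row of Table 8.1-2 (combination) is identical. Section 3.1.2 uses the same grouping for the Stage 1 boundary, at most 1 response "of the first 14 with NSCLC or ovarian cohort".

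**The concern.** The two documents give one cohort different null rates, different target rates and different response counts. A reader who takes the ovarian error rates from the SAP would believe that, with 25 subjects, a drug at the target is placed on the wrong side of the 6/7 line only 7% of the time. That holds only if the target is 40%, and the protocol's ovarian target is 30%. The SAP also leaves two of the five Part 2 cohorts, NSCLC and ovarian, without applicable error rates.

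Protocol Section 8.1 says that the expansion results will inform early decisions and planning. Benchmarks that look well controlled but are not could therefore colour how an ovarian result is read, even though no formal test is planned.

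**Working it through.** **Inputs.** SAP Section 5: n = 25; rates 40% and 20%; 6 or fewer labelled false negative; 7 or more and 8 or more labelled false positive. Protocol Section 8.1 and Table 8.1-1: rates 30% and 15%; n1 = 14, n = 26, Stage 1 boundary r1 = 1.

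**Formulas.** Single stage: P(X ≥ r) = Σ C(n,x) p^x (1−p)^(n−x), summed over x = r to n.

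Two stage: P(at least r in total, Stage 1 passed) = Σ b(x; n1, p) · P(Y ≥ r − x), summed over x = r1+1 to n1, where b is the binomial probability and Y ~ Bin(n − n1, p).

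**Step 1: the SAP's own figures, n = 25.**

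- p = 0.40: P(≥6) = 0.971, P(≥7) = 0.926, P(≤6) = 0.074. The SAP prints 97%, 93% and 7%.
- p = 0.20: P(≥7) = 0.220, P(≥8) = 0.109. The SAP prints 22% and 11%.

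All reproduce. The arithmetic is right for the rates used; the rates are not those of the protocol's ovarian design.

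**Step 2: the protocol's ovarian design, 14/26, r1 = 1.**

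- Early stopping at 15%: 0.85^14 + 14 × 0.15 × 0.85^13 = 0.103 + 0.254 = 0.357 (table: 0.36).
- The table prints no final cut-off. Requiring 6 or more of 26 gives 0.178 at 15% and 0.825 at 30%, matching 0.18/0.82. Requiring 5 or more gives 0.324/0.904, and 7 or more gives 0.082/0.698, so neither fits. The cut-off of 6 is thus inferred.

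**Step 3: the SAP's counts at the protocol's ovarian rates.**

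| Quantity | SAP states | n = 25 | n = 26 with Stage 1 stop |
|---|---|---|---|
| Miss at target, rule ≥7 (6 or fewer) | 7% (at 40%) | 34.1% (at 30%) | 1 − 0.698 = 30.2% |
| False positive, rule ≥7 | 22% (at 20%) | 7.0% (at 15%) | 8.2% |
| False positive, rule ≥8 | 11% (at 20%) | 2.5% (at 15%) | 3.2% |

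For ovarian, then, the SAP understates the chance of a miss and overstates the chance of a false positive. For comparison, the inferred protocol rule of 6 or more of 26 misses 1 − 0.825 = 17.5% at 30%.

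**Step 4: the protocol's single-stage text for 30%, n = 25.** P(≥5) = 0.910 and P(≥6) = 0.807 match the printed 91% and 81%. The printed false-negative rate of 9% for 5 or fewer does not: P(≤5) = 1 − 0.807 = 0.193, while P(≤4) = 1 − 0.910 = 0.090. The 9% belongs to 4 or fewer.

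**The case against.** The best defence is that nothing operational depends on these SAP figures. Section 5 gives illustrative probabilities to support a cohort size. The SAP's efficacy section estimates ORR with a Clopper-Pearson interval and sets no go/no-go rule. Both documents disclaim formal inference or testing. The enrolment decision rests on the protocol's Stage 1 boundary, which is non-binding and which the SAP does not alter. The SAP is version 1.0 and describes only Parts 1 and 2, so it may simply predate the present protocol text.

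Most of this stands, and it rules out two stronger readings.

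- A reader might infer that the SAP's cut-offs would lead the trial to miss an active ovarian drug a third to a half of the time. At a true 30% with n = 25, requiring 7 or more misses 34% and requiring 8 or more misses 51% (30% and 46% with n = 26 and the Stage 1 stop). But no ovarian decision is tied to 7 or 8 responses in either document. The protocol itself lists 7 or more among its false-positive counts for NSCLC and ovarian, so the 34% is not peculiar to the SAP.
- A reader might infer that 6 or 7 responses would be positive under the protocol and negative under the SAP. Seven meets the SAP's own lower count. The readings part mainly at 6, which the SAP labels a false-negative outcome and which meets the protocol's inferred final cut-off. Even there, the SAP also quotes the 97% chance of at least 6.

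The difference between 25 and 26 subjects does not matter either: the protocol uses 25 for its own single-stage ovarian figures.

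What the defence does not remove is that the SAP attaches named false-negative and false-positive rates to the ovarian cohort, and they are not the rates of the cohort as designed. An early version date may explain this but does not correct it.

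**Conclusion.** The point holds as a conflict between the documents. If the protocol's 15% and 30% govern, the SAP's ovarian error rates are wrong by a wide margin: 34% instead of 7% for 6 or fewer responses, and 7% and 2.5% instead of 22% and 11% for the two false-positive counts (n = 25). The SAP has no error rates for 15% versus 30%, which also leaves NSCLC uncovered.

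The consequence is limited to documentation and interpretation. The documents do not support a claim that a decision rule would fail.

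The figures assume independent responses and exact binomial probabilities. The two-stage figures also assume that the Stage 1 stop is followed. The final cut-off of 6 of 26 is inferred from the printed alpha and power. The correction should be made, but it does not threaten the design.

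**What to change.** In SAP Section 5:

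1. Remove ovarian from both mesothelioma sentences.
2. Show the ovarian precision example with NSCLC at 7 of 25 responses (90% interval 14% to 46.2%, already printed there).
3. Add an NSCLC/ovarian paragraph for Part 2: historic 15%, target 30%, 14/26, Stage 1 boundary 1, alpha 0.18, power 0.82. State the final cut-off of 6 or more of 26 and confirm it with the sponsor, since the protocol table does not print it.
4. If single-stage figures are included, compute them afresh. Do not carry over the protocol's 9% for 5 or fewer responses; the value is 19%.

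In protocol Section 8.1, correct that same false-negative figure.

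If 20% versus 40% is truly intended for ovarian, the change belongs in the protocol instead: justify the rates and revise the Section 8.1 text, the ovarian rows of Tables 8.1-1 and 8.1-2, and the Stage 1 boundaries in Sections 3.1.2 and 3.1.3.2 as needed.

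The first route costs a few lines of SAP wording and one corrected number in the protocol, with no change to data collection or enrolment.

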## 6 STUDY PERIODS, TREATMENT REGIMENS AND POPULATIONS FOR ANALYSES

### 6.1 Study Periods

This study consists of four periods: Screening (up to 28 days), Treatment (21 days/cycle for Q3 weekly dosing and 28 days/cycle for Q weekly dosing), Follow-up (60 days), and Survival Follow-up (up to 1 year following the first dose of study drug).

### 6.2 Treatment Regimens

[figure not shown]
In escalation phase, the selection of doses for the two cohorts Part 1A and Part 1B will be based on a modified Fibonacci dose escalation and an mTPI design. BMS-986148 will be administrated

every 3 weeks in Part 1A and weekly for 3 weeks with one week off in Part 1B. In the expansion phase, the optimal regimen from Part 1A or 1B selected upon agreement between the Sponsor/Medical Monitor and Investigators will be adopted in the five cohorts corresponding to these tumor types: mesothelioma, pancreatic, ovarian, NSCLC, and gastric cancer.

The analysis and reporting of safety data will be performed on an as assigned basis at time of study therapy initiation unless otherwise specified. If a subject received the incorrect study medication for the entire period of treatment, the subject will be analyzed in the treatment group associated with the incorrect study medication.

### 6.3 Populations for Analyses

- All Enrolled Subjects: All subjects who signed an informed consent form
- All Treated Subjects: All subjects who received at least one dose of study medication
- Pharmacokinetic Subjects: All subjects who received at least one dose of BMS-986148 and have evaluable serum and plasma concentration data

- 
- Immunogenicity (ADA) Subjects: All treated subjects who have baseline and at least one post baseline immunogenicity assessment
  - ECG Evaluable Population: all treated subjects who had a baseline ECG and at least one on-study ECG.
  - Response Evaluable Population: all treated subjects who had baseline tumor measurement and at least one other tumor measurement after treatment, clinical progression, or death prior to the first on-treatment tumor assessment.

## 7 STATISTICAL ANALYSES

All analyses will be performed in SAS using version 9.2 or higher. Some figures may be generated using S-Plus.

### 7.1 General Methods

Continuous variables will be summarized using descriptive statistics, ie, medians, minimums, maximums, and means with standard deviations/standard errors of the mean. Categorical variables will be summarized by frequencies and percentages. Percentages will be rounded and may not always add up to 100.

### 7.2 Grouping Scheme

Individual subject's data will be listed in the order of subject ID and collection time.

Throughout this analysis plan, a cohort is defined a unique group of subjects identified by study phase (escalation, expansion), dose, dose regimen (Q3W or QW for 3 weeks followed by one week off), and tumor type (if in expansion phase). Summary analyses in this study will be performed with various grouping schemes: cohort, dose+dose regimen, expansion cohorts only, and overall, as shown in [Table 2](#). The scheme of dose + dose regimen consists of groups decided

by the unique combination of dose and dose regimen, regardless of tumor type and study phase. The scheme of expansion cohorts only has the five groups of subjects with different tumor types enrolled into the expansion cohorts.

Grouping for efficacy analyses are further divided by different endpoints as in Table 2, where analyses of BOR and ORR will be done by cohort, and other endpoints will be summarized for expansion cohorts only by tumor type.

Safety analyses will be conducted using data from all cohorts by dose, dose regimen and overall. If appropriate, certain safety endpoints may be summarized with further grouping of tumor type.

**Table 2: Grouping Scheme for Analyses**

Analyses	Dose+Dose Regimen	Cohort	Expansion Cohorts Only	Overall
Subject Disposition		X		X
Demographics and Baseline Characteristics		X		X
Extent of Exposure		X		X
BOR, ORR		X		X
PFSR, ██████████ PFS, DOR			X	
Safety	X			X
Immunogenicity	X			X
PK	X			

### 7.2.1 Study Information

#### Listing:

- Batch number of study drug

### 7.2.2 Accrual

The following will be presented on the All Enrolled Subjects.

#### Summary:

- Number (%) of subjects accrued by country and investigational site: Include country, site number, Principal Investigator's name, number of subjects enrolled, and number of subjects treated

#### Listing:

- Subjects accrued by country and investigational site

### **7.2.3 Relevant Protocol Deviations**

Relevant Protocol Deviation is a deviation that could potentially affect the interpretability of the study results. Any change to the SAP that involves analysis/reporting of Relevant Protocol Deviations should be made prior to breaking the blind (or prior to the database lock for open-label study).

Non-programmable relevant eligibility and on-treatment protocol deviations, as well as significant (both programmable and non-programmable) will be reported through [REDACTED] listings. The following programmable deviations from inclusion and exclusion criteria will be considered as relevant protocol deviations and a listing will be provided, subject to data availability and applicability.

#### **Inclusion Criteria**

- 1) Only subjects with high expression of mesothelin in the tumor tissue will be enrolled in the expansion phase
- 2) All subjects must have at least one measurable lesion at baseline by CT or MRI as per RECIST v1.1 or Modified RECIST criteria for malignant pleural mesothelioma
- 3) ECOG performance status score 0-1

#### **Exclusion Criteria**

- 4) Grade 2 or higher eye disorders (inclusive of all NCI CTCAE v4.03 criteria). Mild eye symptoms such as blurry vision, either age-related or due to ocular or systemic disorder (e.g. diabetes, dry eyes, cataracts, uncorrected refraction abnormality) may be allowed at the discretion of the ophthalmologist if deemed as not constituting a predisposition to drug-induced corneal deposits and blurry vision.
- 5) Physical and Laboratory Test Findings
  - a) Inadequate bone marrow function defined as:
    - i) Absolute neutrophil count (ANC) < 1,500 cells/mm^3 ;
    - ii) Platelet count < 100,000 cells/mm^3;
    - iii) Hemoglobin < 9.0 g/dL
  - b) Subjects with a stable chronic transfusion requirement (e.g. due to cumulative toxicity from previous therapy) of no more than once per month will be allowed if the trough hemoglobin is > 8.0 g/dL.
  - c) Inadequate hepatic function defined as:
    - i) Total bilirubin > 1.5 times the institutional ULN (except known Gilbert's syndrome);
    - ii) Alanine transaminase (ALT) or aspartate transaminase (AST) > 3 times the institutional ULN.
  - d) Inadequate renal function defined as:
    - i) Blood creatinine > 1.5 times the institutional ULN
  - e) Any of the following on 12-lead electrocardiogram (ECG) prior to study drug administration, confirmed by repeat.

- i)  $QRS \geq 120$  msec, except right bundle branch block
- ii)  $QTcF \geq 450$  msec for males,  $\geq 470$  msec for females, except right bundle branch block

### **7.3 Study Population**

#### **7.3.1 Subject Disposition**

##### **Summary:**

- Pre-treatment period: The number (%) of subjects of the following will be summarized on the All Enrolled Subjects.
  - All enrolled into the study
  - Entering the treatment period
  - Enrolled but not entering the treatment period together with the reasons
- End of treatment period and of study: The number (%) of subjects of the following will be summarized by cohort and overall, based on the All Treated Subjects.
  - All treated subjects
  - Subject completing the treatment period
  - Reasons for not completing the treatment period
  - Subjects continuing in the study
  - Subjects not continuing in the study
  - Reasons for not continuing in the study
- All related data will be listed

#### **7.3.2 Demographics and Other Baseline Characteristics**

##### **Summary:**

Descriptive statistics will be summarized for the following baseline characteristics for all treated subjects by cohort and overall.

- Age (in years) ; age category ( $<65$ ,  $\geq 65$ )
- Gender
- Race
- Ethnicity (if applicable)
- Height
- Weight
- BMI
- ECOG performance status
- Baseline mesothelin expression
- Disease characteristics such as stage and factors that might affect response to therapy and possibly relevant variables (eg, smoking)
- Prior cancer therapy

**Listing:**

- All relevant data, generally variables listed above by cohort.

